4.2.2 Patients unable to give consent personally

For patients unable to express valid consent personally, consent will be obtained in the same way as for patients able to express consent, but through a respondent (witness, legal guardian or family member/cohabitant of the patient) who will act on behalf of the patient according to the following cases:

- a) If a patient is of sound mind and verbal consent but is temporarily unable to sign and date the consent form in his or her own hand, for example due to a concomitant unfavorable medical condition, a witness may sign the consent form in the signature space. It is understood that the witness:
 - must not be part of the study group as defined in the "Register of personnel dedicated to the Clinical Investigation" compiled by the Sponsor during the monitoring visit dedicated to the opening of the Center in agreement with the Investigator responsible for the investigation;
 - it must be impartial, i.e. not the bearer of its own interest in the patient's enrolment in the investigation.
- b) If a patient has previously been declared by a court or legal judgment unable to provide for his or her interests, or the patient is legally disqualified and therefore has a legal representative, the consent will be expressed by the legal representative himself who, if he or she accepts the patient's participation in the investigation, must also sign and date the consent form.
- c) Given the expected type of patients who can be enrolled in the survey, i.e. elderly patients mostly of very advanced age, as already found in normal clinical practice, there is a high possibility that many of these patients are in fact unable to provide for their own interests but that they have not previously been declared interdicted by a judicial or legal ruling, therefore not equipped with a legal representative. This condition would lead to the exclusion from the investigation of a significant percentage of eligible patients due to the impossibility of collecting informed consent (an inclusion criterion would be missing). In order to safeguard the achievement of an adequate sample size of the study population in a reasonable time, and in order to limit as much as possible the selection of patients (patients of very advanced age are the most representative in proximal femur fractures), if a patient is in fact unable to provide for his or her own interests but is not legally prohibited, The information will be addressed to the patient's family member or cohabitant, who may express consent on behalf of the patient by signing and dating the form in the appropriate signature space.

Note:

- In this condition, the patient's family member or cohabitant is entitled to act pursuant to Art. 105 paragraph 3, Legislative Decree 101/2018 "*When, in the context of processing for scientific research purposes, specific circumstances identified by the rules of ethics are such as to allow one subject to respond in the name and on behalf of another, as a family member or cohabitant, the information may also be provided through the respondent*".

4.3 Obtaining informed consent in emergency conditions

Whenever objectively possible, the consent form will always be signed and dated by the patient or respondent (witness, legal guardian or family member/cohabitant of the patient) prior to verification of inclusion criteria, which is the first procedure under this Protocol.

In emergency situations, i.e. when due to:

- the patient's medical condition and/or;
- the clinical context in which the Investigator and/or will operate;
- of the impossibility of the respondent to be immediately present.

It will not be possible to provide information on the survey and receive any clarifications; the patient or the respondent will be informed as soon as possible about the possibility of participating in this observational survey and will be able to express their consent even later according to the methods described above.

5 Information for the general practitioner

The Sponsor with the documentation relating to this Clinical Investigation will provide the Investigators with a pre-printed information letter to the treating physician containing all relevant information regarding this observational investigation. Once the patient inclusion and exclusion criteria have been verified, if the patient will indeed be included in the investigation, the Investigator will fill in the pre-printed letter with the patient's data and deliver this letter to the patient himself or to the respondent subject who will be in charge of delivering it for information to the general practitioner.

6 Any news regarding the medical device under investigation

In the event that, during the course of this Clinical Investigation, the Investigator or the Sponsor becomes aware of news regarding the Chimaera system, deriving from this investigation or from market reports (*complaints*), which may influence the decision of the patient (or the respondent) to participate in the Clinical Investigation, it will be the Investigator's responsibility to promptly inform each subject already enrolled in the Investigation.

It is understood that, following this new information made available, the patient (or respondent) or the Investigator may refuse to continue the investigation at any time they wish without prejudice to subsequent care.

7 Vulnerable population and treatment in emergency circumstances

Given the observational nature of this Clinical Investigation, this protocol does not provide for any special procedures, i.e. procedures that are different from those already implemented through normal clinical practice for the management of vulnerable populations and emergency circumstances.

8 Preclinical Evidence and Previous Clinical Experience

Orthofix Srl has developed and placed on the European market the Chimaera after carrying out an evaluation of the clinical performance and safety of the medical device on the basis of biomechanical tests and clinical data obtained from scientific publications on equivalent products (on request, more details available in Technical File A.1.10 archived at the Sponsor).

The outcome of this pre-market assessment established that the Chimaera meets the necessary requirements for CE marking, in particular it has an acceptable risk/benefit ratio when used according to the manufacturer's indications for use.

This observational clinical investigation is the first clinical trial carried out on the Chimaera system, so no clinical reports are available from previous clinical trials carried out by the Sponsor.

Sales data show that to date the treatments carried out in Europe with Chimaera are more than 3000: the frequencies of serious complications received by Orthofix Srl through the passive medical device vigilance system are lower than those reported in the literature for equivalent nails on the market for several years. This first evidence seems to confirm the efficacy and safety of the technical characteristics integrated into the device; however it must be integrated with clinical data that will be collected through the present observational investigation.

9 Information related to the clinical investigation

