4.2.1 Patients able to give consent personally

Before taking part in the Clinical Investigation, any eligible patient capable of expressing valid consent personally, understood to be of sound mind and willing and able to affix his/her signature and date on the form:

1. You will be informed of the possibility, voluntary, of participating in the clinical investigation and that, if you agree to participate, you may refuse to continue the investigation at any time without prejudice to subsequent treatment;
2. will be informed about the potential benefits for the scientific community and for other patients deriving from the increase in the scientific knowledge generated by the survey;
3. if interested, through a specific information notice you will receive adequate information on the purpose of the clinical investigation, its characteristics (observational and non-interventional), the schedule of visits, the expected duration of the same, your responsibilities and the methods of collecting and processing clinical data;
4. he/she will be given the necessary time to receive from the Investigator all clarifications and additional information he/she deems necessary;
5. if he decides to participate in the clinical investigation, before carrying out the first visit provided for by the Protocol, he will sign and give the informed consent of which he will keep a copy.

It is understood that:

- as specified in the form for obtaining consent, by signing, the patient expresses his/her consent both for participation in the survey and for the collection and processing of clinical data;
- if deemed necessary in the best interest of the patient's health, the Investigator may decide to discontinue participation in the investigation without the consent of the patient who will be informed of the decision and the related reasons.

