9.2 Design of the Clinical Investigation

The present clinical investigation is of the following type:

- Observational (as ascertained in the feasibility phase, the procedures reported in this Protocol are part of the normal clinical practice of the Centers involved);
- post-market (the medical device observed has a CE mark and is already used in the Sites involved);
- prospective (clinical data will be collected from patients who will be treated with the observed device after signing the informed consent);
- uncontrolled (only the medical device under study will be observed);
- non-randomized (since the Survey is observational and uncontrolled, a randomized assignment of the medical device is not applicable);
- multicenter (the Survey will be conducted in 8 Centers);
- national (the Sites involved are all located in Italy).

Considering the purpose and design described above, this Clinical Investigation falls within the type of studies defined as "*Post Market Clinical Follow-up (PMCF) study*" (more details in MEDDEV 2.12/2 rev. 2).

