9.6.2 Exclusion criteria

A patient will be considered not eligible for participation if:

- he/she is undergoing surgery to address the sequelae of a previously treated fracture;
- he/she has been diagnosed with a pathological fracture of oncologic origin (primary tumour or skeletal metastasis);
- he/she has been diagnosed with a fracture in the diaphyseal and/or distal region of the femur;
- he/she has been diagnosed with an open proximal femoral fracture (type II or III according to the Gustilo and Anderson classification);
- he/she has been diagnosed with multiple fractures (including bilateral proximal femoral fractures);
- during the preoperative or intraoperative phase, it is decided to treat the fracture with the long version of the Chimaera nail and/or with non-telescopic (fixed-length) cephalic screws;
- he/she has a medical condition that constitutes a contraindication to treatment with Chimaera according to the manufacturer's instructions for use;
- he/she has a suspected or confirmed hypersensitivity/allergy to any component of the device that comes into contact with the patient;
- he/she presents with any clinical condition that, in the opinion of the Investigator, could interfere with the Clinical Investigation procedures or compromise patient safety;
- he/she is concomitantly treated with a non-permitted device that cannot be removed without compromising patient safety;
- he/she is participating in another clinical study or has participated in another clinical study within 3 months prior to signing the informed consent form.

9.7 *Expected Number of Patients to be Enrolled*

Considering the high proportion (approximately 25%) of anticipated premature withdrawals in this patient population, in order to obtain a sample of 300 patients completing the Investigation, a total of 400 patients are planned to be enrolled across 8 sites. Accordingly, each site is expected to enrol approximately 50 patients over a period of 6–8 months (estimate based on the current frequency of Chimaera use as reported by the sites during the feasibility phase).

9.8 *Enrolment Timepoint*

Each eligible patient able to provide consent personally will be considered enrolled in the Clinical Investigation at the time of signing and dating the informed consent form, in accordance with the procedures for collection described in this Protocol.

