9.11 Medical-Surgical Procedures and Follow-up of the Clinical Investigation

After obtaining informed consent, the physician will include in the study those patients who, at the screening visit (Visit 0), meet all selection criteria. During the screening visit, the Investigator will also collect demographic data and the patient's medical history.

Enrolled patients, as would also occur if they chose not to participate in the present Investigation, will undergo the surgical procedure (Visit 1) required for the application of the investigational medical device (Chimaera), which marks the beginning of the treatment period.

Following the surgery, the patient will attend five subsequent visits. The first three visits after the surgical procedure are part of the treatment period and are:

- the visit performed at hospital discharge (Visit 2), which, unless complications occur, will take place within 10 days after the date of surgery. During this visit, the physician will perform routine assessments to confirm that the operation and postoperative course have proceeded appropriately;
- the following two visits (Visits 3 and 4), were conducted at 1 month and 3 months after the date of surgery, respectively. These visits conclude the treatment period which, in the absence of complications, is expected to be within 8–12 weeks from the date of surgery, with the consolidation of the treated proximal femoral fracture. Healing will be assessed by the Investigator through radiographic evaluation, performing a qualitative assessment of bone density at the fracture site and the alignment of the bone fragments. Starting from Visit 4 and at all subsequent visits, the Investigator will also complete the Bowers & Parker functional score (efficacy measure) to assess the patient's functional recovery.

For these patients, device removal is not planned unless required due to serious adverse events necessitating a second surgical procedure to complete the treatment of the fracture (safety measure). Once the treatment period is concluded, the follow-up period begins, during which two visits will be conducted (Visits 5 and 6), respectively at 6 months and 1 year after the date of surgery. During these visits, clinical data will be collected to monitor the progression of fracture consolidation, the patient's functional recovery, and the occurrence of any medium-term adverse events.

[figure not shown]

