9.14 Predictable factors that can compromise results

The procedures described in this Protocol are part of the normal clinical practice of the Centers involved. In fact, this clinical investigation is observational so it will not change the clinical protocols currently in use in the Centers involved, nor does it involve additional risks for patients and investigators.

In the present clinical investigation, given the type of patients who will be enrolled, two factors are known that could compromise the outcomes and the interpretation of the results, namely:

- For some very elderly patients who have difficulty moving and with impaired cognitive ability, for example due to senile dementia or advanced neurodegenerative diseases, the assessment of functional recovery may be more difficult.

The Bowers & Parker Functional Score⁷ chosen to assess the patient's functional recovery in terms of pain, walking ability and social independence, as described by the authors, precisely because it could be used in high probability on patients unable to answer reliably, it is composed of questions that can also be answered by the patient's companion (e.g. cohabitant, family member, caregiver, social health worker, etc.), understood as a person who lives in close contact with the patient. The companion can also answer by phone and, given the difficulty of moving this type of patient, this possibility will be very useful to limit the loss of data on the patient's functional recovery in the follow-up period.

- The mortality rate of enrolled patients is about 10% at 10 days after surgery and can reach up to 36% at 1 year. Therefore, a high percentage (25% on average) of non-assessable patients, i.e. discontinued before the end of the treatment period for supposed recovery (scheduled for the check-up visit in the third month after the operation), is expected in the present clinical investigation.

In order to increase the probability of reaching the expected sample size, i.e. 300 evaluable patients, i.e. who will complete at least the scheduled follow-up visit at the third month after the operation (Visit 4), the Sponsor has planned the enrollment of 400 patients and has agreed with the Investigators on a patient replacement procedure described below.

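### The visit table lets consent and selection fall up to a week after surgery, against the stated consent-first order, so early deaths and re-operations could go unenrolled and uncounted

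*Combined protocol and SAP*

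**What the plan says.** Three sections describe a cohort that consents first and is operated on afterwards.

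- Section 4.2.1: "before carrying out the first visit provided for by the Protocol, he will sign and give the informed consent".
- Section 9.2, defining the study as prospective: "clinical data will be collected from patients who will be treated with the observed device after signing the informed consent".
- Section 9.11: "After obtaining informed consent, the physician will include in the study those patients who, at the screening visit (Visit 0), meet all selection criteria". Surgery follows as Visit 1.

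Two places allow something else.

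- The table in 9.13 gives Visit 0 a window of Day 0 ± 1 week and puts surgery on Day 0. Visit 0 is the only column in which informed consent is ticked.
- Section 4.3 opens with a default: "Whenever objectively possible, the consent form will always be signed and dated by the patient or respondent" before the inclusion criteria are verified. It then makes an exception where the patient's condition, the clinical setting or an absent respondent prevents this. The patient or respondent is to be informed as soon as possible and "will be able to express their consent even later according to the methods described above". No latest time is given.

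Section 9.8 sets the moment of entry. A patient able to consent "will be considered enrolled in the Clinical Investigation at the time of signing and dating the informed consent form"; for others it is the representative's signature. Section 9.16 promises to analyse patients who discontinue or are replaced, but they must have been enrolled first. The primary endpoint (9.4) is the percentage of patients with a second operation for device-related serious adverse events within 6 months.

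**The concern.** Read as written, the 9.13 window makes consent and selection a week after implantation acceptable for any patient, not only in an emergency. Two things follow for a single-arm study whose main result is one percentage.

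First, a patient who dies or is re-operated before a signature is obtained may never enter the study. The protocol asks for no log of eligible implanted patients, no consecutive enrolment and no report of when consent was given relative to surgery. The final report could not show how many such patients there were.

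Second, criteria checked after surgery are checked with the early course known. One exclusion in 9.6.2 is discretionary: a clinical condition that the investigator thinks could interfere with study procedures or compromise safety. An early complication could be read as meeting it.

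The early period matters in this population. Section 9.14 states: "The mortality rate of enrolled patients is about 10% at 10 days after surgery". Section 2 gives about 10% at 30 days for patients over 75. The two figures disagree and need reconciling, but either makes early loss relevant.

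**Working it through.** **1. The plan's own figures.** The upper limits in Section 18 are two-sided exact binomial limits, BetaInv(0.975; x+1, n−x). With x/n = 3/100, 4/100, 8/160, 15/250 and 28/400, this gives 8.518%, 9.926%, 9.614%, 9.703% and 9.958%, matching every row. Enrolment is 300/(1 − 0.25) = 400, as stated. The arithmetic of the plan is sound; the issue is who enters the percentage.

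**2. Room before the sizing target is crossed.** Section 18 expects at most 6% and sizes the study for an upper limit below 10%. In 300 evaluable patients:

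| Events | Upper 95% limit |
|---|---|
| 18 (6%) | 9.32% |
| 19 | 9.71% |
| 20 | 10.11% |

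**3. Early re-operations never enrolled.** Start from 18/300 enrolled and add the missed patients to numerator and denominator:

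- 1 missed: 19/301 = 6.31%, upper limit 9.68%
- 2 missed: 20/302 = 6.62%, upper limit 10.04%
- 6 missed: 24/306 = 7.84%, upper limit 11.45%

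**4. Early deaths without re-operation never enrolled.** Add to the denominator only:

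- 7 missed: 18/307 = 5.86%, upper limit 9.11%
- 33 missed: 18/333 = 5.41%, upper limit 8.41%

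Here the enrolled figure of 6% is too high, not too low.

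**5. Both together.** Let p be the true rate among all implanted patients, d the share consenting after surgery, e the share of their re-operations that occur before consent and are lost, and m the share of them who die before consent without re-operation and are lost. Then

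observed rate = p(1 − de) / (1 − dpe − dm).

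The documents give none of d, e or m directly. With p = 6% and assumed ranges d = 25–75% and e = 10–30%, take m from 0 to 7.1%. The upper value is the 10-day mortality figure scaled to 7 days at constant hazard, 1 − 0.9^(7/10); the 30-day figure gives 1 − 0.9^(7/30) = 2.4%.

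- Lowest (d = 75%, e = 30%, m = 0): 0.0465/0.9865 = 4.71%
- Highest (d = 25%, e = 10%, m = 7.1%): 0.0585/0.98075 = 5.96%
- Outside that range (d = 100%, e = 10%, m = 10%): 0.054/0.894 = 6.04%

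**6. What decides the direction.** The observed rate exceeds p when 1 − de > 1 − dpe − dm, that is when m > e(1 − p) = 0.94e, whatever d is. With m = 2.4% the bias turns upward if e is below 2.4/0.94 = 2.6%. With m = 7.1% it does so if e is below 7.1/0.94 = 7.6%. The protocol says nothing on how early re-operations fall, so the sign cannot be settled from it.

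Steps 4 to 6 assume that early deaths would count in the denominator. Section 18 does not define it. If only patients reaching Visit 4 counted, early deaths would be left out in any case and the upward effect would drop away.

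**The case against.** The other side has several fair points.

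- **Section 4.3 does not itself place consent after surgery.** Its reference point is the check of inclusion criteria, it asks for information as soon as possible, and it never mentions surgery. Only the table cell does so explicitly, and that cell, in the enrolment column before Visit 1, may be a symmetric window entered by habit. This stands as a reading of intent, but sites work from the table.
- **Survival is not strictly required.** A reader might infer that a late-consent patient has to live long enough to be approached. The documents do not support that: sections 4.2.2, 4.3 and 9.8 let a respondent or representative sign. Section 4.2.2(c) adds the family route partly to limit selection. Equally, nothing ensures that a signature is sought after an early death.
- **An understated risk is not established.** It is tempting to conclude that early failures are selectively missing and the rate is too low. Step 6 shows that the sign depends on quantities the protocol does not give.
- **A large loss is not established.** If all 400 consented at the end of the window, 2.4% to 7.1% early mortality would imply about 10 to 28 treated patients never enrolled. That would require every site to disregard 4.2.1, 9.2 and 9.11.
- **Event-free time before entry adds little.** The endpoint is a simple percentage, not a person-time rate, and the nominal window is at most 7 days out of 6 months.
- **There is no pass mark.** Section 18 states no hypothesis and no safety threshold, so crossing 10% is not a failed test. It is, however, the precision the study was sized to reach.

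What remains is the contradiction between 9.13 and the three consent-first sections, the missing outer limit in 4.3, and the absence of any means to see the effect.

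**Conclusion.** The concern holds as an internal contradiction with an unquantified consequence. The 9.13 window permits consent and selection up to a week after surgery; 4.2.1, 9.2 and 9.11 do not; and 4.3 permits deferral with no stated limit and no link to the window. Because entry is dated from signature, early deaths and re-operations could be missing from the primary percentage, and post-operative entrants can be selected on early outcome.

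Confidence is high for the contradiction and low for the size. Under the assumed shares, a true 6% would be observed as about 4.7% to 5.96%, with 6.04% in an extreme case, so neither size nor direction is fixed. The firmest statement is one of sensitivity: at the planned 6% in 300 patients, two unenrolled early re-operations are enough to move the upper limit from 9.32% to 10.04%. If few patients consent after surgery, the effect will be small, but the plan as written would not show that.

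**What to change.** 1. In 9.13, end the Visit 0 window at Day 0 before surgery, in line with 4.2.1, 9.2 and 9.11. Keep post-operative consent only as the 4.3 exception, flagged in the data collection form, and give that exception a stated outer limit agreed with the ethics committees.
2. In Section 18, report the primary percentage with its exact 95% interval for all enrolled patients. As a sensitivity analysis, report it for those consented before surgery. Give the number consented after surgery and the distribution of days from surgery to consent.
3. If the ethics committees permit, have each site keep an anonymous count of otherwise eligible short-nail patients not enrolled because of death or re-operation before consent. This is secondary: section 4.1 ties data collection to signed consent, so even a count may need review.

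Items 1 and 2 need little new data: consent forms are already dated and fully monitored (Section 10), and follow-up visits are timed from the surgery date. The costs are a somewhat wider interval in the pre-operative-consent subset and a protocol amendment. Under Section 15, an amendment classed as substantial suspends the investigation until a new favourable opinion is given, so the change is best made before enrolment starts or combined with another amendment.
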